#### Power Statement:

Standardized mean differences of 0.75 will be considered operationally relevant effect sizes for this comparison based our previous motion sickness mitigation protocols using the oculovestibular recoupling methodology

(Cevette et al. 2012). Based on the equation above, we will have 80% statistical power to detect standardized mean differences (two-sided tests) of 0.75 with an alpha error level of 0.05 with a sample of 16 subjects. A target of at least 30 subjects is requested to account for incomplete data sets.

### Endpoints

**Primary:** Our project will deliver a non-pharmaceutical countermeasure approach using galvanic vestibular reduction (GVR) that can be customized to mitigate G-transitional induced motion sickness while optimizing sensorimotor and cognitive performance.

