Our first specific aim is to evaluate the effect of timing and magnitude on the administration of our nonpharmaceutical treatment to motion sickness. While we have previously demonstrated that our approach can mitigate motion sickness if introduced prior to the provocative stimuli, one of the goals of this study is to determine the efficacy if we administer the treatment following the onset of symptoms. Validating the efficacy following symptom onset would alleviate the need for certifying the device to be worn within the landing suit and greatly enhance flexibility to implement this treatment during recovery operations. Our first hypothesis is that efficacy of galvanic vestibular reduction to reduce motion sickness severity will depend on the timing and magnitude of the administration. We will test this hypothesis by exposing subjects to provocative Coriolis crosscoupling stimuli on a rotating chair using a repeated measures counter-balanced design to compare motion sickness severity across three treatment interventions: prior to stimulus (symptom) onset, following symptom onset, and placebo control. The GVR amplitude will be customized based on individual sensitivity. Symptom severity will be assessed using both subjective reports and objective autonomic measures (electrogastrography and cardiac interbeat intervals). We expect that the most effective administration will be GVR delivered prior to the onset of symptoms, but that it will continue to be more effective relative to placebo control even if delivered following symptom onset.

Our second specific aim is to evaluate the effect of GVR amplitude on functional fitness task performance. One disadvantage of pharmaceutical approaches is that increased drug dosage is often accompanied by sedative side

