movements will be cued every 10 sec, alternating between pitch forward (chin resting on chest) and pitch backward (head upright). This timing allows for subjects to use the joystick to record motion perception associated with each pitch forward and backward movement. There will be a short pause following each set of 9 forward/backward movements (3 min) to review symptoms with the subject, although motion sickness symptoms will be obtained throughout the test protocol using verbal reports. Subject will continue making head movements until the motion sickness endpoint (moderate nausea) or the maximum number of paired forward/backward head movements (90) has been reached.

**Galvanic Vestibular Reduction (GVR) application:** We will use a repeated measures design to compare motion sickness severity for each subject across the three treatment interventions: prior to stimulus onset, following symptom onset, and placebo control. For each session, the participant will be instrumented for GVR prior to rotation. The amplitude (up to 2.5 mA) will be customized based on individual sensitivity (see below). The order of the three sessions will be counter-balanced across subjects. For the “*prior to*” session, the GVR will be initiated just prior to the chair motion. For the “*midpoint*” session, the GVR will be initiated following 4 of 10 sets of movements or the onset of slight nausea, whichever occurs first. For the “*control*” session, the subject will be instrumented without turning on the GVR throughout the testing.

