#### Data Analysis Plan:

We hypothesize that efficacy of galvanic vestibular reduction to reduce motion sickness severity will depend on the timing of the administration, being more effective when administered prior to stimulus (symptom) onset. For specific aim 1 we will use repeated measures ANOVA to examine changes in symptom severity, test duration (terminated at moderate nausea), and recovery to baseline across three levels: prior to stimulus (symptom) onset, following symptom onset, and placebo control. For specific aim 2 we hypothesize that functional task performance will decline with increasing levels of galvanic vestibular reduction amplitude. We will use repeated measures ANOVA to examine changes in cognitive performance, dynamic posturography, and dual tracking performance across up to 5 levels of GVR amplitude. Sample size estimates are based on: (1) the expected variability ( $s^2$ ) in the response parameters, (2) the alpha ( $\alpha$ , type I) error level, or probability of incorrectly concluding there is an effect when responses are equivalent, (3) the magnitude of the effects to be detected between the means ( $\mu_1, \mu_2$ ), and (4) the certainty (statistical power,  $1 - \beta$ ) with which the effect is to be detected. Sample sizes can be calculated based on the expected standardized differences ( $\Delta$ ) between conditions (Fisher and Van Belle 1993).

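### The only primary endpoint is a project deliverable, and the planned three-condition F test does not test Aim 1's pairwise claims, including that GVR started after symptom onset beats control

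*Combined protocol and SAP*

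**What the plan says.** **Endpoints.** The only entry is labelled primary: "Our project will deliver a non-pharmaceutical countermeasure approach using galvanic vestibular reduction (GVR) that can be customized to mitigate G-transitional induced motion sickness", followed by a clause on performance. It describes what the project will produce, not something measured on a subject.

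**Data Analysis Plan.** For Aim 1, repeated-measures ANOVA is to "examine changes in symptom severity, test duration (terminated at moderate nausea), and recovery to baseline across three levels": prior, following symptom onset, and placebo control. The three outcomes are not ranked. No contrast, post-hoc test or multiplicity rule is given. The hypothesis is that efficacy depends on timing, "being more effective when administered prior to stimulus (symptom) onset".

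**Research Question and Aims.** "one of the goals of this study is to determine the efficacy if we administer the treatment following the onset of symptoms". The expectation is that prior GVR works best, but that "it will continue to be more effective relative to placebo control even if delivered following symptom onset".

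**Motion sickness recordings.** Up to three subjective severity measures are proposed, with the choice left to pilot testing. Table II collects all three: two after each set and one at the end of the session.

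**Motion sickness test paradigm.** Head movements continue "until the motion sickness endpoint (moderate nausea) or the maximum number of paired forward/backward head movements (90) has been reached".

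**Power Statement.** "Standardized mean differences of 0.75 will be considered operationally relevant effect sizes for this comparison based our previous motion sickness mitigation protocols". The plan then claims "80% statistical power to detect standardized mean differences (two-sided tests) of 0.75 with an alpha error level of 0.05 with a sample of 16 subjects", and requests at least 30 subjects to allow for incomplete data. Subject Information gives a target of 40. No dropout rate is stated.

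**The concern.** Two things are missing that a reader needs before the data are seen: which outcome decides Aim 1, and which comparison on that outcome.

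The Aim 1 claims are pairwise: midpoint against control, and prior against midpoint. A three-level F test asks only whether the three means are all equal. It can reject because of the prior session alone and so say nothing about treatment after symptom onset. No result is fixed in advance as the one that would establish the post-onset claim. The analyst is left free to choose among three outcomes, up to three severity scales and three pairs of conditions.

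The power statement does not close the gap. It refers to a comparison of means in the setting of motion sickness mitigation, but names neither the outcome nor the two conditions.

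**Working it through.** **Inputs.** Standardized difference 0.75, two-sided alpha 0.05, n = 16, and at least 30 requested (Power Statement); three conditions and repeated-measures ANOVA (Data Analysis Plan). *Assumptions:* 0.75 is in units of the SD of the within-subject difference (the plan does not say which SD), and sphericity holds.

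**1. The plan's own figure.** For a paired t test the noncentrality is 0.75 × √n.
- n = 16: 0.75 × 4 = 3.0, df 15, critical value 2.131, power **80.1%** (n = 15 gives 77.1%). The stated 16 is reproduced.
- n = 30: noncentrality 4.11, df 29, power **97.8%**.

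So 16 is correct for one unadjusted paired contrast.

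**2. Power of the planned F.** With the SD of a difference equal to 1, the residual variance is 0.5. The noncentrality is λ = n × Σ(μᵢ − μ̄)² / 0.5, with df 2 and 2(n − 1).
- Midpoint equal to control (0.75, 0, 0) or to prior (0.75, 0.75, 0): the sum of squares is 0.375, so λ = 0.75n.
- Midpoint halfway (0.75, 0.375, 0): the sum of squares is 0.28125, so λ = 0.5625n.

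| Pattern | λ, n = 16 | F power, n = 16 | λ, n = 30 | F power, n = 30 |
|---|---|---|---|---|
| Midpoint equals either end | 12.0 | 84.7% | 22.5 | 99.0% |
| Midpoint halfway | 9.0 | 72.5% | 16.9 | 95.7% |

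**3. What a significant F says about the post-onset claim.** Take prior at 0.75 and midpoint with no effect. F is significant 84.7% (n = 16) or 99.0% (n = 30) of the time. The paired test of midpoint versus control is significant about 5% of the time, which is its false-positive rate.

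**4. A gated alternative.** Test F at 0.05. Only if it is significant, test the three paired contrasts at two-sided 0.05 each. With exactly three conditions this holds the familywise level at 5%. If all three means are equal, the gate limits the error to 5%. If they are not all equal, at most one pairwise null can be true, and it is tested at 5%. Simulation under the full null (200,000 runs) gave at least one rejection 5.0% of the time.

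Simulated power under the gate:

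| Scenario | n = 16 | n = 30 |
|---|---|---|
| Prior and midpoint both 0.75: both confirmed against control | 68% | 96% |
| Midpoint halfway: midpoint vs control confirmed | 28% | 51% |
| Prior vs control alone, midpoint at either end | 76% | 97% |
| Prior vs control alone, midpoint halfway | 71% | 96% |

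**5. Why a gate and not a fixed sequence.** Consider the order prior vs control, midpoint vs control, then prior vs midpoint. With prior 0.75, midpoint null and n = 30, the last step is reached and passed only about 4% of the time, because midpoint vs control must be significant first. The same contrast has 97.8% power alone and about 97.4% under the gate. The timing hypothesis is the one the Data Analysis Plan states, so it should not depend on midpoint vs control.

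**6. Several outcomes.** Three independent outcomes each tested at 0.05 give 1 − 0.95³ = 14.3% chance of at least one false positive. Positive correlation lowers this. The true count is open because the severity scale is open.

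**The case against.** **Pairwise comparison is implied.** The sample-size text speaks of differences between two means and of two-sided tests, and the aims say in words what is expected. An analyst would probably look at the condition means and run follow-up tests, and a null midpoint effect would then be visible. This has force: the documents do not say that a significant F would be taken as proof of post-onset efficacy, and that misreading is a possibility, not a plan. What stands is that no outcome, pair of conditions or error rule is written down, so those choices could be made after seeing the data.

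**The study may be exploratory.** The template text under Data Analysis says that endpoint analysis plans are appropriate even then, and this plan states hypotheses and a power target.

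**Stronger readings that the documents do not support.** A reader might infer that 16 is miscalculated or that the study is underpowered. The figure is correct for one paired contrast, and enrolment targets are 30 or 40. A reader might also take post-onset efficacy to be the sole purpose; the aims call it one of the goals. The equation mentioned in the Power Statement is absent from the text supplied, which may be an extraction loss and is not counted against the plan.

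**Conclusion.** The point holds as a specification gap and should be corrected before analysis. The primary entry cannot be analysed. The planned F test can be significant 84.7% (n = 16) to 99.0% (n = 30) of the time when midpoint GVR has no effect, so by itself it cannot answer the post-onset question. Nor does it test prior against later administration. The 80% power figure belongs to a paired contrast that the analysis plan never names; it is not the power of the planned F.

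These figures assume 0.75 in units of the SD of the within-subject difference, sphericity and normal data. The number of completers is unknown, so results are shown for 16 and 30.

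**What to change.** **Endpoints.** Name one Aim 1 outcome that is already collected, with its scale and time point; the choice is the sponsor's. State how a session that stops early at moderate nausea enters the analysis. Label the other Aim 1 outcomes secondary.

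**Data Analysis Plan.** Keep the repeated-measures F test at 0.05 as a gate. If it is significant, test prior vs control, midpoint vs control and prior vs midpoint as paired contrasts at two-sided 0.05 each. This protects the 5% level on the primary outcome only, and relies on sphericity for the gate. State that Aim 2 and the secondary outcomes lie outside it, or how they are covered.

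**Power Statement.** Restate the 80% as the power of the named paired contrast on the named outcome, before the gate is applied.

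**Before defining the midpoint contrast.** The GVR application paragraph starts midpoint GVR after four sets or at slight nausea, whichever comes first; Table II keeps it off for the first four sets. These passages must be reconciled.

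**Cost.** No new measurements, but sponsor decisions are needed. The gate lowers the power of one contrast at 0.75 from 80% to about 71–76% with 16 completers, and from 98% to about 96–97% with 30. Confirming both contrasts against control at 0.75 has about 96% power with 30 completers but 68% with 16. If midpoint is only halfway, midpoint vs control has about 51% and 28%, so a smaller post-onset benefit could well be missed.
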